**9.4 Patient Withdrawal from Study**

During the course of the study, it is possible that patients may withdraw or be withdrawn from the study. Factors that may lead to a withdrawal from the study may include, but are not limited to the following:

- Patient Withdrawal.....At any time a patient may voluntarily withdraw from the study. This withdrawal will not affect their future medical treatment or benefits.
- Patient Lost to Follow-Up.....Should a patient be classified as lost to follow-up, efforts to contact the patient should be made.
- Physician Decision.....Should a physician decide that continuing in the study is detrimental to the health and welfare of the patient, the patient may be withdrawn from the study.
- Medical Reason.....Should the patient condition deteriorate the patient may be withdrawn from the study to allow for proper medical care.

**10.0 Risk/Benefit Analysis**

**10.1 Risk associated with Stereotactic Body Radiotherapy for head and neck tumors**

**10.1.1** Acute toxicities reported to occur as a result of SBRT for head and neck tumors include, but are not limited to:

- General malaise
- Radiation dermatitis – dryness, tanning, redness, itching
- Localized hair loss
- Mucositis
- External otitis
- Otitis Media
- Xerostomia

- Mastoiditis
- Weight loss
- Pharyngitis
- Vertigo

**10.1.3** Late toxicities reported to occur as a result of SBRT for head and neck tumors include, but are not limited to:

- Radionecrosis of the temporal bone, skull base, mandible
- Radionecrosis of brain tissue
- Soft tissue necrosis
- CVA
- Cranial nerve neuropathy
- Ipsilateral hearing loss
- Vocal cord paralysis
- Nasal hemorrhage
- Localized skin fibrosis, edema, and/or ulceration
- Radiation-induced malignancy (ex. Fibrosarcoma)

## **10.2 Minimization of Risks**

Although the risks outlined in Section 9.3 may occur, the likelihood of serious events occurring is considered uncommon as long as certain precautions are taken. The potential risks have been minimized by strict compliance with normal tissue dose constraints as described in Sections 6.3.

## **10.3 Potential Patient Benefits**

- 10.3.1** Ability to offer effective aggressive local therapy to patients with recurrent unresectable head and neck cancers who have received prior wide-field radiation
- 10.3.2** Reduction in amount of radiation delivered to adjacent normal structures
- 10.3.3** Reduced treatment duration compared to standard-fractionation radiation therapy

## **10.4 Justification of the Study**

Patients who have locally recurrent or persistent malignant head and neck cancer after definitive conventionally fractionated radiation therapy pose a therapeutic challenge since complete surgical resection is often not feasible and surrounding critical normal tissues have typically received close to maximum tolerable radiation doses. High dose, precisely targeted radiation with stereotactic body radiotherapy, which delivers minimal additional radiation dose to nearby normal tissues can produce durable local control and palliation of local symptoms such as pain. In addition, some benign head and neck tumors which are located near the skull base and/or involve critical vasculature also pose a surgical challenge. These tumors appear to have a reasonably high local control probability with radiation therapy. SBRT is advantageous in this setting by limiting the dose to adjacent normal tissues in patients who otherwise have a long life expectancy.

## **10.5 Statistical Analysis**

- 10.5.1** The overall survival and local control rates will be analyzed.
- 10.5.2** The incidence rate for any serious adverse events will be calculated.

#### **HOW MANY PEOPLE WILL TAKE PART IN THE STUDY?**

Approximately 50 people are expected to participate in this clinical study.

**KARNOFSKY PERFORMANCE SCALE**

100	Normal; no complaints; no evidence of disease
90	Able to carry on normal activity; minor signs or symptoms of disease
80	Normal activity with effort; some signs or symptoms of disease
70	Cares for self; unable to carry on normal activity or do active work
60	Requires occasional assistance, but is able to care for most personal needs
50	Requires considerable assistance and frequent medical care
40	Disabled; requires special care and assistance
30	Severely disabled; hospitalization is indicated, although death not imminent
20	Very sick; hospitalization necessary; active support treatment is necessary
10	Moribund; fatal processes progressing rapidly
0	Dead

**ZUBROD PERFORMANCE SCALE**

0	Fully active, able to carry on all pre-disease activities without restriction (KPS 90-100)
1	Restricted in physically strenuous activity but ambulatory and able to carry out work of a light or sedentary nature. For example, light housework, office work (KPS 70-80)
2	Ambulatory and capable of all self-care but unable to carry out any work activities. Up and about more than 50% of waking hours (KPS 50-60)
3	Capable of only limited self-care, confined to bed or chair 50% of more of waking hours (KPS 30-40)
4	Completely disabled. Cannot carry on any self-care. Totally confined to bed or chair (KPS 10-20)

### 12.3 Appendix III

#### Common Terminology Criteria for Adverse Events v3.0 (CTCAE)

Toxicity	GRADE				
	1	2	3	4	5
CONSTITUTIONAL					
Fatigue	Mild fatigue over baseline	Moderate or causing difficulty performing some ADL	Severe fatigue interfering with ADL	Disabling	-
Fever	100.4-102.2°F	102.3-104.0°F	> 104.0°F for ≤ 24 hr	> 104.0°F for > 24 hr	Death
Weight loss	5 - < 10% of baseline	10 - < 20% of baseline	≥ 20% of baseline; tube feeding or TPN indicated	-	-
PAIN					
Pain due to radiation	Mild pain not interfering with function	Moderate pain; pain or analgesics interfering with function, but not interfering with ADL	Severe pain; pain or analgesics severely interfering with ADL	Disabling	-
Myositis (inflammation or damage of muscle)	Mild pain not interfering with function	Pain interfering with function, but not interfering with ADL	Pain interfering with ADL	Disabling	Death
SKIN					
Radiation dermatitis	Faint erythema or dry desquamation	Moderate to brisk erythema; patchy moist desquamation, mostly confined to skin folds and creases; moderate edema	Moist desquamation other than skin folds and creases; bleeding induced by minor trauma or abrasion	Skin necrosis or ulceration of full thickness dermis; spontaneous bleeding from involved site	
Telangiectasia	Few	Moderate number	Many and confluent	-	-
Ulceration	-	Superficial ulceration < 2 cm size; local wound care; medical intervention indicated	Ulceration ≥ 2 cm size; operative debridement, primary closure or other invasive intervention indicated (ex. Hyperbaric oxygen)	Life-threatening consequences; major invasive intervention (ex. Complete resection, tissue reconstruction, flap, grafting)	Death
Induration	Increased density on palpation	Moderate impairment of function not interfering with ADL; marked increase in density and firmness on palpation with or without minimal retraction	Dysfunction interfering with ADL; ery marked density, retraction or fixation	-	-
SOFT TISSUE					
Fibrosis	Increased density, "spongy" feel	Increased density with firmness or tethering	Increased density with fixation of tissue; operative intervention indicated; interfering with ADL	Life-threatening; disability; loss of limb; interfering with vital organ function	Death
Soft Tissue Necrosis	-	Local wound care; medical intervention indicated	Operative debridement or other invasive intervention indicated (ex. Hyperbaric oxygen)	Life-threatening consequences; major invasive intervention indicated (ex. Tissue reconstruction, flap, or grafting)	Death

Osteonecrosis	Asymptomatic, radiographic findings only	Symptomatic and interfering with function, but not interfering with ADL; minimal bone removal indicated (minor sequestrectomy)	Symptomatic and interfering with ADL; operative intervention or hyperbaric oxygen indicated	Disabling	Death
AUDITORY/EAR					
Hearing	-	Hearing loss not requiring hearing aid or intervention (i.e., not interfering with ADL)	Hearing loss requiring hearing aid or intervention (i.e., interfering with ADL)	Profound bilateral hearing loss (>90 dB)	-
Otitis, external ear (non-infectious)	External otitis with erythema or dry desquamation	External otitis with moist desquamation, edema, enhanced cerumen, or discharge; tympanic membrane perforation; tympanostomy	External otitis with mastoiditis; stenosis or osteomyelitis	Necrosis of soft tissue or bone	Death
Otitis, middle ear (non-infectious)	Serous otitis	Serous otitis, medical intervention indicated	Otitis with discharge; mastoiditis	Necrosis of canal soft tissue or bone	Death
GI TRACT					
Dental, periodontal disease	Gingival recession or gingivitis; limited to bleeding on probing; mild local bone loss	Moderate gingival recession or gingivitis; multiple sites of bleeding on probing; moderate bone loss	Spontaneous bleeding; severe bone loss with or without tooth loss; osteonecrosis of maxilla or mandible	-	-
Dental, teeth	Surface stains, dental caries; restorable, without extractions	Less than full mouth extractions; tooth fracture or crown amputation or repair indicated	Full mouth extractions indicated	-	-
Xerostomia	Symptomatic (dry or thick saliva) without significant dietary alteration; unstimulated saliva flow > 0.2 ml/min	Symptomatic and significant oral intake alteration (e.g.; copious water, other lubricants, diet limited to purees and /or soft, moist foods) unstimulated saliva flow 0.1 to 0.2 ml/min	Symptoms leading to inability to adequately aliment orally; IV fluids, tube feedings, or TPN indicated; unstimulated saliva <0.1 ml/min	-	-
Nausea	Loss of appetite without alteration in eating habits	Oral intake decreased without significant weight loss, dehydration, or malnutrition; IV fluids indicated < 24 hr	Inadequate oral caloric or fluid intake; IV fluids, tube feedings, or TPN indicated ≥ 24 hr	Life-threatening consequences	Death
Vomiting	1 episode in 24 hr	2-5 episodes in 24 hr; IV fluids indicated < 24 hr	≥ 6 episodes in 24 hr; IV fluids or TPN indicated ≥ 24 hr	Life-threatening consequences	Death
Dysphagia	Symptomatic, able to eat regular diet	Symptomatic, and altered eating/swallowing (e.g., altered dietary habits, oral supplements); IV fluids indicated < 24 hours	Symptomatic, and severely altered eating/swallowing (e.g., inadequate oral caloric or fluid intake); IV fluids, tube feedings, or TPN indicated ≥ 24 hours	Life-threatening consequences (e.g./ obstruction, perforation)	Death
Mucositis (clinical exam)	Erythema of the mucosa	Patchy ulcerations or pseudomembranes	Confluent ulcerations or pseudomembranes; bleeding with minor trauma	Tissue necrosis; significant spontaneous bleeding; life threatening consequences	Death
Esophagitis	Asymptomatic, pathologic, radiographic or endoscopic findings only	Symptomatic; altered eating/swallowing (e.g. altered dietary habits, oral supplements) IV fluids indicated < 24 hours	Symptomatic and severely altered eating/swallowing (e.g. inadequate oral caloric or fluid intake) IV fluids, tube feedings, or TPN indicated ≥ 24 hours	Life-threatening consequences	Death
Ulceration	Asymptomatic,	Symptomatic; altered GI	Symptomatic and	Life-threatening	Death

	radiographic or endoscopic findings only	function (altered dietary habits, oral supplements); IV fluids indicated < 24 hr	severely altered GI function (inadequate oral caloric or fluid intake); IV fluids, tube feedings, or TPN indicated ≥ 24 hr	consequences	
Bleeding	Mild, intervention (other than iron supplements) not indicated	Symptomatic and medical intervention or minor cauterization indicated	Transfusion, interventional radiology, endoscopic, or operative intervention indicated	Life-threatening consequences; major urgent intervention indicated	Death
Perforation	Asymptomatic radiographic findings only	Medical intervention indicated; IV fluids indicated < 24 hr	IV fluids, tube feedings, or TPN indicated ≥ 24 hr; operative intervention indicated	Life-threatening consequences	Death
Stricture	Asymptomatic radiographic findings only	Symptomatic; altered GI function (altered dietary habits, vomiting, bleeding, diarrhea); IV fluids indicated < 24 hr	Symptomatic and severely altered GI function (altered dietary habits, diarrhea, or GI fluid loss); IV fluids, tube feedings, or TPN indicated ≥ 24 hr; operative intervention indicated	Life-threatening consequences; operative intervention requiring complete organ resection	Death
Fistula	Asymptomatic; radiographic findings only	Symptomatic; altered GI function (ex. Altered dietary habits, diarrhea, or GI fluid loss); IV fluids indicated < 24 hr	Symptomatic and severely altered GI function (ex. Altered dietary habits, diarrhea, or GI fluid loss); IV fluids, tube feedings, or TPN indicated ≥ 24 hr	Life-threatening consequences	Death
Taste Alterations	Altered taste but no change in diet	Altered taste with change in diet (e.g.; oral supplements); noxious or unpleasant taste; loss of taste	-	-	-
LYMPHATICS					
Lymphatics (head and neck)	Localized to dependant areas, no disability or functional impairment	Localized facial or neck edema with functional impairment	Generalized facial or neck edema with functional impairment (e.g.; difficulty in turning neck or opening mouth compared to baseline)	Severe with ulceration or cerebral edema; tracheotomy or feeding tube	Death
NEUROLOGY					
Brachial plexopathy	Asymptomatic	Symptomatic, not interfering with ADL	Symptomatic, interfering with ADL	Disabling	Death
CNS Necrosis	Asymptomatic, radiographic findings only	Symptomatic, not interfering with ADL; medical intervention indicated	Symptomatic and interfering with ADL; hyperbaric oxygen indicated	Life-threatening; disabling; operative intervention indicated to prevent or treat CNS necrosis/cystic progression	Death
Myelitis	Asymptomatic, mild signs (e.g.; Babinski's or Lhermitte's sign)	Weakness or sensory loss not interfering with ADL	Weakness or sensory loss interfering with ADL	Disabling	Death
OCULAR/VISUAL					
Cataract	Asymptomatic, detected only on exam	Symptomatic, with moderate decrease in visual acuity (20/40 or better); decreased visual function correctable with glasses	Symptomatic with marked decrease in visual acuity (worse than 20/40); operative intervention indicated (e.g.; cataract surgery)	-	-
Dry eye syndrome	Mild, intervention not	Symptomatic, interfering	Symptomatic or decrease	-	-

	indicated	with function but not interfering with ADL; medical intervention indicated	in visual acuity interfering with ADL; operative intervention indicated		
Retinopathy	Asymptomatic	Symptomatic, with moderate decrease in visual acuity (20/40 or better)	Symptomatic with marked decrease in visual acuity (worse than 20/40)	Blindness (20/200 or worse)	-
SECONDARY MALIGNANCY	-	-	Non-life-threatening basal or squamous cell carcinoma of the skin	Solid tumor, leukemia, or lymphoma	Death

**12.4 Appendix IV**

**DEMOGRAPHIC FORM – Page 1 of 1**

1. Name \_\_\_\_\_ (last) \_\_\_\_\_ (first)
  2. Date of Birth \_\_\_\_ / \_\_\_\_ / \_\_\_\_\_
  3. RT Number \_\_\_\_\_
  4. Race:  Asian       Caucasian       Black       Other, specify \_\_\_\_\_
  5. Zubrod PS:  0       1       2       3
  6. Radiation oncologist: \_\_\_\_\_
  7. Medical oncologist: \_\_\_\_\_
  8. Surgeon: \_\_\_\_\_
  9. Tumor category:  Benign Head and Neck tumor, specify type \_\_\_\_\_  
 Malignant Head and Neck Tumor, specify type \_\_\_\_\_
  10. Maximum tumor diameter: \_\_\_\_\_ cm
  11. AJCC Staging Classification:  I       II       III       IV       N/A (recurrence)
  12. Status of distant metastatic disease:  No distant metastatic disease  
 Stable distant metastatic disease  
 Progressive metastatic disease
  13. Pretreatment CT scan:    Date of CT scan \_\_\_\_\_
  14. Prior Head and Neck radiation:       No       Yes, explain \_\_\_\_\_
  15. Pre-SBRT chemotherapy:  No  
 Yes, regimen & last cycle date \_\_\_\_\_
- Person completing form: Signature \_\_\_\_\_ Print Name \_\_\_\_\_

**12.5 Appendix V**

**TREATMENT FORM – Page 1 of 1**

1. Name \_\_\_\_\_ (last) \_\_\_\_\_ (first)

2. RT Number \_\_\_\_\_

3. Tumor Details:

Tumor category:  Benign Head and Neck tumor, specify type \_\_\_\_\_

Malignant Head and Neck Tumor, specify type \_\_\_\_\_

Lesion #	Location	Maximum Diameter (cm)	GTV Volume (cc)	CTV Margin (cm)	PTV Margin (cm)			PTV Volume (cc)
					AP	RL	CC	
1								
2								
3								
4								
5								

4. Treatment Portal Design:

Static gantry angle (coplanar), specify number of fields \_\_\_\_\_

Static gantry angle (non-coplanar), specify number of fields \_\_\_\_\_

Dynamic arc (coplanar), specify number of arcs \_\_\_\_\_

Dynamic arc (non-coplanar), specify number of arcs \_\_\_\_\_

5. Dose-Fractionation Scheme:

Lesion #	Total Dose (Gy)	Dose per Fx (Gy)	# Fx	Prescription IDL (%)	D max (Gy)	BED α/β=10 (Gy)	BED α/β=3 (Gy)	CI
1								
2								
3								
4								
5								

6. Dose to Normal Tissues:

Prior Head and Neck radiation:  No (Table 1)  Yes (Table 2)

Table 1 (No prior Head and Neck radiation)

Normal Tissue	D max (Gy)
Optic Chiasm	
Optic Nerve	
Brainstem	
Spinal Cord	
Brachial Plexus	

Internal Carotid Artery in Cavernous Sinus	
Oculomotor Nerves in Cavernous Sinus	
Esophagus	
Skin	

Table 2 (Prior Head and Neck radiation)

Normal Tissue	D max (Gy)	Prior RT D max (Gy)*	Total D max (Gy) (D max + Prior RT D max )
Optic Chiasm			
Optic Nerve			
Brainstem			
Spinal Cord			
Brachial Plexus			
Internal Carotid Artery in Cavernous Sinus			
Oculomotor Nerves in Cavernous Sinus			
Esophagus			
Skin			

\*Estimation of the dose (Gy) may be required

7. Premedication:

- None
- Anti-nausea, specify drug \_\_\_\_\_, dose \_\_\_\_\_ mg,
- Decadron, specify dose \_\_\_\_\_ mg
- Analgesics, specify drug \_\_\_\_\_, dose \_\_\_\_\_ mg
- Acetaminophen, specify dose \_\_\_\_\_ mg

Person completing form: Signature \_\_\_\_\_ Print Name \_\_\_\_\_

**12.6 Appendix VI**

**FOLLOW-UP VISIT FORM – Page 1 of 2**

1. Name \_\_\_\_\_ (last) \_\_\_\_\_ (first)

2. RT Number \_\_\_\_\_

3. Date of Visit: \_\_\_\_ / \_\_\_\_ / \_\_\_\_

4. CT scan date: \_\_\_\_ / \_\_\_\_ / \_\_\_\_

5. Radiation Therapy related adverse events

Adverse Event	CTC V3.0 Grade	Timing	Treatment	Comments
ACUTE				
 Fatigue				
 Fever				
 Nausea				
 Vomiting				
 Loss of appetite				
 Weight loss				
 Esophagitis				
 Alopecia				
 Radiation dermatitis				
 Musculoskeletal pain				
 Mucositis				
 Hoarseness				
 Pneumonitis				
 Xerostomia				
 External otitis				
 Otitis Media				
 Mastoiditis				
 Dizziness				
LATE				
 Radionecrosis of temporal bone, skull base, mandible				
 Radionecrosis of brain tissue				
 CVA				
 Cranial nerve neuropathy				
 Hearing loss				
 Vocal cord paralysis				
 Nasal hemorrhage				
 Hypothyroidism				
 Esophageal stricture/perforation				
 Brachial plexopathy				
 Telangiectasia				
 Skin Ulceration				
 Skin/SubQ Tissue Fibrosis				
 Soft Tissue Necrosis				
 Radiation-induced Malignancy				

5. Serious adverse event?  No  Yes, submit report to HIC

6. Has systemic therapy been given?  No  Yes

If yes, list therapy  
Agent(s)

Start Date

Stop Date

_____	____/____/____	____/____/____
_____	____/____/____	____/____/____
_____	____/____/____	____/____/____

7. CT scan since last follow-up visit?  No  Yes, date \_\_\_\_/\_\_\_\_/\_\_\_\_

Tumor Response:  Complete response  
 Partial response  
 Stable disease  
 Progressive disease

8. PET/CT scan since last follow-up visit?  No  Yes, date \_\_\_\_/\_\_\_\_/\_\_\_\_

Tumor Response:  Complete response  
 Partial response  
 Stable disease  
 Progressive disease

8. Disease Status

No evidence of tumor  
 Local recurrence within the treatment volume  
 Progressive liver disease outside the treatment volume  
 Distant recurrence, specify site \_\_\_\_\_

Date of Diagnosis

____/____/____
____/____/____
____/____/____

9. Additional treatment for recurrent disease

Surgical excision  Yes  No  
Chemotherapy, agents \_\_\_\_\_  Yes  No  
Other, specify \_\_\_\_\_  Yes  No

Date of surgery \_\_\_\_/\_\_\_\_/\_\_\_\_

Start date \_\_\_\_/\_\_\_\_/\_\_\_\_

Start date \_\_\_\_/\_\_\_\_/\_\_\_\_

10. Death?  No  Yes, date \_\_\_\_/\_\_\_\_/\_\_\_\_ Cause? \_\_\_\_\_

Person completing form: Signature \_\_\_\_\_ Print Name \_\_\_\_\_

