## **2.0 Objectives**

This study will evaluate the local control rates as well as acute and late toxicity rates of stereotactic body radiotherapy (SBRT) for the treatment of benign and malignant head and neck tumors.

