### **2.3 End Points**

**2.3.1** Primary endpoints will be local control rate and complication rate

- Local recurrence is defined as cancer recurrence within the target volume.
- Local control rate will be evaluated by imaging techniques, physical exam and biopsy, if applicable.
- Evaluation of complication rates (see Section 9.3 for definitions)

**2.3.2** Secondary endpoint will be overall survival

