### **9.3 Toxicity**

**9.3.1** The investigator will report and record all serious adverse events that occur. Adverse events should be reported using the CTC grading system (Appendix III).

**9.3.2** Examples of anticipated acute adverse events include:

- General malaise
- Radiation dermatitis – dryness, tanning, redness, itching
- Localized hair loss
- Mucositis
- External otitis
- Otitis Media
- Xerostomia
- Mastoiditis

- Weight loss
- Pharyngitis
- Vertigo

**9.3.3** Examples of anticipated late adverse events include:

- Radionecrosis of the temporal bone, skull base, mandible
- Radionecrosis of brain tissue
- Soft tissue necrosis
- CVA
- Cranial nerve neuropathy
- Ipsilateral hearing loss
- Vocal cord paralysis
- Nasal hemorrhage
- Localized skin fibrosis, edema, and/or ulceration
- Radiation-induced malignancy (ex. Fibrosarcoma)

**9.3.4** Reporting of unanticipated or serious adverse events will be reported according to the institutions IRB policy. An unanticipated adverse effect is defined as follows:

Any serious adverse effect on health or safety or any life-threatening problem or death caused by, or associated with, stereotactic body radiotherapy, if that effect, problem, or death was not previously identified in nature, severity, or degree of incidence in the investigational plan or application (including a supplementary plan or application), or any other unanticipated serious problem associated with a treatment that relates to the rights, safety, or welfare of subjects.

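### The graded adverse event table on the follow-up form admits only radiation-related events and records no attribution, so for non-serious toxicity a judgement of cause acts as a hidden filter

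*Protocol*

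**What the plan says.** Section 2.3.1 states: "Primary endpoints will be local control rate and complication rate". It sends the reader to Section 9.3 for the definition of complications. Section 2.0 sets the aim as local control together with the acute and late toxicity rates of SBRT.

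Section 9.3 contains a rule for serious events ("The investigator will report and record all serious adverse events that occur"), an instruction to grade by CTC, and lists of anticipated acute and late events given as examples. Its only wording on causation is in 9.3.4, which defines an unanticipated effect for reporting to the IRB. Nothing there says which events, grades or causes make a complication.

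Section 10.5.2 gives the one stated safety analysis: "The incidence rate for any serious adverse events will be calculated".

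The Follow-up Visit Form (Appendix VI) has a checkbox table under the heading "Radiation Therapy related adverse events". Its columns after the event name are "CTC V3.0 Grade", timing, treatment and comments. Below it is a separate serious adverse event question, answered No or "Yes, submit report to HIC", with no condition on cause. Later items collect systemic therapy with dates, disease status, and date and cause of death.

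**The concern.** The table heading makes relatedness a condition of entry, but relatedness itself is not recorded. Someone who thinks a non-serious event is due to tumor, an earlier course of radiation or chemotherapy can reasonably read the heading as a reason not to tick the box. The table would then look the same as if the event had not happened.

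Cause is hard to judge in this population, on the protocol's own description:

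- Section 1.0 says chondrosarcomas tend to involve the lower cranial nerves. The form lists cranial nerve neuropathy and vocal cord paralysis as late events.
- Two of the three groups in Section 2.2.2 have had earlier radiation, and Section 10.4 says nearby tissues are often close to tolerance. The heading does not say whether it means study SBRT or the earlier course.
- Section 8.0 allows chemotherapy before and after SBRT. Fatigue, nausea and weight loss are on the list.
- Section 9.1 schedules no toxicity assessment before treatment, so no graded baseline is planned against which to check attribution later.

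At stake is the toxicity evidence for the hypothesis in Section 2.1.1 that complication rates are acceptable. An analysis plan can choose a numerator, but it cannot restore events that were never entered.

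**Working it through.** The protocol states no complication rate, reference rate or power, so there is no figure to reproduce. The check is a comparison of texts, followed by an illustration.

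**Step 1: which events reach which record**

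| Type of event | Where it is recorded | Filtered by cause? | Attribution recorded? |
|---|---|---|---|
| Serious, any cause | Serious-event item on the form; 9.3.1; incidence in 10.5.2 | No | No field on the form |
| Non-serious, judged radiation-related | Graded table | Passes the heading | No |
| Non-serious, judged not radiation-related | No graded entry required | Yes, by the heading | No |

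The third row is the gap. Sections 2.0 and 2.3.1 speak of toxicity and complication rates, not of serious events alone. Listed events such as hearing loss or neuropathy may never be serious.

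**Step 2: direction**

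Let *r* be the proportion of patients with a listed event of any cause, and *f* the share of those patients whose event is left off as unrelated. The recorded rate is *r*(1 − *f*), which cannot exceed *r*. Against an any-cause rate the filter therefore works only downward. Against the true SBRT-caused rate its direction is unknown: correct attribution would reproduce that rate, and wrong attribution could miss it on either side.

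**Step 3: illustrative size**

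The sample consent text expects about 50 participants. The event counts and the shares left off are assumptions; none comes from the protocol. Intervals are exact (Clopper-Pearson) 95%.

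| Patients with an event | Share left off | Recorded | Rate (95% CI) |
|---|---|---|---|
| 10 | 0% | 10/50 | 20% (10.0–33.7%) |
| 10 | 20% | 8/50 | 16% (7.2–29.1%) |
| 10 | 40% | 6/50 | 12% (4.5–24.3%) |
| 10 | 50% | 5/50 | 10% (3.3–21.8%) |
| 10 | 60% | 4/50 | 8% (2.2–19.2%) |
| 5 | 0% | 5/50 | 10% (3.3–21.8%) |
| 5 | 60% | 2/50 | 4% (0.5–13.7%) |
| 15 | 0% | 15/50 | 30% (17.9–44.6%) |
| 15 | 60% | 6/50 | 12% (4.5–24.3%) |

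The any-cause serious-event incidence in 10.5.2 does not change in any of these rows.

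**The case against.** The strongest reply is that the safety analysis the protocol actually states is not touched. Section 9.3.1 asks for all serious events, the form has its own unrestricted line for them, and 10.5.2 counts them without regard to cause. This stands. A reader might infer from the heading that the form as a whole loses unrelated events, or that it contradicts 9.3.1. Neither follows, because the word *all* in 9.3.1 governs serious events and the form has a place for those.

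A reader might also infer that this table alone supplies the primary complication rate. No section says so. It is a reasonable inference for non-serious events only, since no other graded form is shown.

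Next, the heading may be just a label over a checklist of known radiation toxicities, with no intention that anything be omitted, and the comments column could hold doubts about cause. This is a fair reading. But the heading then bears two readings, and two people could complete the form differently.

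Third, competing causes are partly documented through prior radiation, systemic therapy dates and disease status, and the office-visit records exist. Some retrospective review would therefore be possible, and it would be too strong to say that omitted events leave no trace anywhere. But these fields are not linked to individual events, and the study table would not show which patients to review.

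Finally, a treatment-related rate suits the aim in Section 2.0. This is true, and an attribution column would produce that rate in a form that can be checked.

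**Conclusion.** The point holds for non-serious graded toxicity. The table heading restricts entry by cause, the cause is not recorded, the radiation course is not specified, and Section 9.3 does not say whether a complication needs attribution. The serious-event incidence is unaffected.

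The size is unknown. A fall from 20% to 10% needs 10 of about 50 participants with an event and half of those left off; both are assumptions chosen to show the arithmetic.

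It is also tempting to say that unblinded treating clinicians are judging their own results in SBRT's favor. The protocol does not mention blinding, and the form refers only to the person completing it. An unblinded assessor is a fair inference from a single-site, non-randomized design, but favorable judgement is not shown, and the point does not depend on it.

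This is a modest defect. It is worth correcting before data are collected because it decides which data will exist.

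**What to change.** 1. In Appendix VI, retitle the table *Adverse events (all, regardless of cause)*.
2. Add an attribution column: study SBRT, prior radiation, tumor, systemic therapy, other. Include a degree of certainty so that *at least possibly related* can be derived.
3. State in Section 9.3 that the complication rate is reported twice: for events of any cause, and for events at least possibly related to study SBRT.

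The cost is one heading, one column, one sentence and slightly more data entry. The any-cause rate will look less favorable than a related-only rate, which is why both should be shown.

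### The follow-up form's adverse event table has no other/specify row and lacks rows for events named in Section 9.3 or graded in Appendix III, so non-serious complications may be under-recorded.

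*Protocol*

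**What the plan says.** Protocol 2.3.1 states: "Primary endpoints will be local control rate and complication rate". It refers the reader to Section 9.3 for what counts as a complication, and Section 2.0 sets acute and late toxicity rates as part of the objective.

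Section 9.3 gives open lists, introduced by "Examples of anticipated acute adverse events include" and "Examples of anticipated late adverse events include". Section 9.3.1 requires all serious adverse events to be recorded and reported, and sends grading of adverse events to Appendix III (CTCAE v3.0).

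Appendix III grades terms that 9.3 does not name. Examples are myelitis (grade 3: "Weakness or sensory loss interfering with ADL"), dysphagia (grade 1: "Symptomatic, able to eat regular diet") and retinopathy.

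Appendix VI, the follow-up visit form, collects events in a table headed "Radiation Therapy related adverse events". It has pre-printed rows with columns for grade, timing, treatment and comments. A separate yes/no item asks about a serious adverse event and, if yes, calls for a report. Section 10.5.2 plans to calculate the incidence of serious adverse events.

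**The concern.** An open definition is being collected on a fixed list. A site that fills in the form as printed has nowhere to enter a non-serious event that lacks a row. Missing rows can lose events but cannot add them, so any error lowers the complication rate. That is also the direction that favors the hypothesis in 2.1.1 of acceptable complication rates. Non-serious events not written down at the visit may be hard to recover later.

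The gap looks like an oversight. The same form offers an other/specify line for additional treatment of recurrence, and the demographic form offers one for race.

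**Working it through.** The protocol states no complication rate, target or sample size calculation, so there is no figure to reproduce. The check compares three lists item by item: the events in 9.3, the terms in Appendix III, and the rows in Appendix VI. Near-synonyms were matched: malaise with fatigue, hair loss with alopecia, vertigo with dizziness, osteonecrosis with radionecrosis of bone, and CNS necrosis with radionecrosis of brain.

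**Step 1. Rows on the form.** 18 acute + 15 late = 33. None is an other/specify row.

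**Step 2. Section 9.3 against the form.** Of 11 acute bullets, 10 have a row; pharyngitis does not. All 10 late bullets have a row, but one only in part: it names edema alongside fibrosis and ulceration, and only the latter two have rows.

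**Step 3. Appendix III against the form.** Appendix III grades 37 terms.

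| Status on the form | Terms | Count |
|---|---|---|
| Direct or synonymous row | remainder | 22 |
| No direct row, partial overlap with another row | induration, myositis, pain due to radiation, GI bleeding | 4 |
| No near match | myelitis, retinopathy, cataract, dry eye, dysphagia, taste alteration, two dental terms, head and neck lymphatics, fistula, GI ulceration | 11 |

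37 − 22 = 15 terms have no direct row, and 15 − 4 = 11 have no near match. The 11 is the more cautious count.

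**Step 4. Overlap of the two gaps.** Myelitis, retinopathy and dysphagia are in Appendix III but not in 9.3 (0 of 3). Pharyngitis is in 9.3 but not in Appendix III. Only edema is named in 9.3, graded in Appendix III (under lymphatics) and absent from the form.

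**Step 5. Scale.** Let k be the number of patients whose only complication is non-serious and unlisted, and so goes unrecorded. The consent form expects about 50 participants. The fall in the any-complication rate is 100 × k / 50 = 2k percentage points.

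| k (assumed) | Fall in rate |
|---|---|
| 0 | 0 points |
| 1 | 2 points |
| 2 | 4 points |
| 5 | 10 points |

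The documents give no basis for choosing k.

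**The case against.** The strongest reply is that the important events are safe. Section 9.3.1 requires every serious adverse event to be recorded, the form has its own serious-event item, and 10.5.2 analyzes serious events, none of which depends on the pre-printed rows. This stands. A reader might infer that a disabling myelitis or blindness would drop out of the results; the documents do not support that.

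It does not dispose of the point, because the endpoint is not confined to serious events. Section 2.0 speaks of toxicity rates generally, and the 9.3 examples include mild skin changes, hair loss and malaise. The serious-event item also has no field for term or grade.

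Second, nothing forbids reporting beyond the printed rows. Section 9.3.1 does not limit which adverse events are graded, toxicity assessment is suggested at each follow-up visit (9.1), and the table has a comments column. This is fair as to intent. But the comments column belongs to the pre-printed rows and does not prompt for anything else.

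Third, neighboring rows catch part of the gap. Appendix III grades esophagitis partly by altered swallowing, much as it grades dysphagia, and its dermatitis grading mentions edema. A patient with dysphagia who also has mucositis is still counted as having a complication. This lowers the likely k, but the unlisted event itself remains uncounted.

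Two other strong readings fail. One is that 11 of 37 terms, about 30%, means a similar share of complications is lost: that counts labels, not events. The other is that the primary rate is understated as a matter of fact: that would need event frequencies the protocol does not give. Nor are form rows without a counterpart in 9.3, such as pneumonitis, an error, since the 9.3 lists are only examples.

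**Conclusion.** The point holds in limited form. Used as printed, the form gives non-serious unlisted events no place to be recorded, and this may bias a primary endpoint low. Two omissions (pharyngitis, edema) are from the section that defines complications; about 11 more are from the grading appendix alone.

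The size is not computable: about 2 points per affected patient at 50 patients, and possibly zero. The conclusion rests on two assumptions. The first is that the complication rate counts non-serious events. Sections 2.0, 2.3.1 and 9.3 suggest so, but 10.5.2 names only serious ones, and if only those count, the effect is nil. The second is that staff record what the rows prompt for. The matching of near-synonyms is a judgment, which is why 11 is given as approximate.

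**What to change.** In the Appendix VI adverse event table, add a row for other events, asking for the term and the CTCAE v3.0 grade, in both the acute and the late section. Add rows for the missing terms from 9.3 and Appendix III: at least pharyngitis, edema, dysphagia, myelitis, visual toxicity and fistula. Keep all existing rows; removing those that 9.3 does not name (brachial plexopathy or hypothyroidism, for instance) would reduce capture.

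Make the change prospectively. It requires a form revision only, with no change to visits or treatment. The cost is a slightly longer form and possibly a higher reported complication rate.
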